8. RISKS/DISCOMFORTS

8.1 Risks associated with Idebenone therapy

There is considerable clinical trial and post-marketing experience indicating that idebenone is well tolerated and has a good safety profile. Safety data are available from 311 patients with Friedreich's Ataxia (FRDA) or Leber Hereditary optic neuropathy (LHON) treated with idebenone at doses of between 900 and 2250 mg/day. No noteworthy imbalances in the distribution of adverse events (AEs) were observed for the comparison of idebenone or placebo. The most commonly observed adverse reactions were gastrointestinal disorders. The following reactions were observed in more than one patient: headache, diarrhea, nausea and dyspepsia. The following reactions were not observed in more than one patient at the recommended doses: white blood cell count decrease, disturbance in attention, angina pectoris, vomiting, reflux oesophagitis, musculoskeletal chest pain, myalgia, upper abdominal pain.

Clinical trials with idebenone have previously been performed in indications other than FRDA and LHON, predominantly in older patient populations (mainly in Alzheimer's dementia). Besides some of the reactions listed above, patients in these trials showed the following reactions uncommonly (between 1/1000 and 1/100): sleep disorders, nervousness, dizziness, changes in hepatic laboratory values and influenza-like symptoms. These reactions may be more likely in this elderly study population with CNS impairment and more concomitant medications.

The IPPoMS trial will randomize up to 85 PP-MS patients either to idebenone (2250 mg/day) or to placebo. This study is under the supervision of a Data Safety Monitoring Board. By July 2012 approximately 20 patients had been treated with study medication. Five Serious Adverse Events (SAEs) have been reported on this trial to date but all were considered unrelated to study medication and the DSMB had raised no safety concerns with regard to the conduct of the study.

Idebenone at high doses (60-75 mg/kg/day or about 3600-4500 mg/day) may cause orange discoloration of urine in few patients. It is unclear if this will occur at the dose of 2250mg/day. The orange discoloration of urine is completely harmless and urine will be monitored every 6 months by urinalysis in order to ensure that hematuria or hemoglobinuria is not mistaken for the orange discoloration due to idebenone.

8.2 Risks of lymphocytapheresis

Adverse reactions associated with lymphocytapheresis include vasovagal syncope with needle insertion and rare hypotension secondary to volume depletion. Because of the controlled nature of these procedures hypotension is unlikely. Exclusion of patients with a history of cardiovascular disease further reduces the risk of this complication. The blood thinner used to prevent blood clots from apheresis can cause mild muscle cramps. If these side effects occur, we can slow down blood flow or use a different blood thinner. If the symptoms do not go away, the apheresis can be stopped. There may also be bruising at the site of needle insertion. Infection is a potential risk, but is unlikely

due to the closed system and the maintenance of sterile technique. The Blood Bank has extensive experience with these procedures and has encountered no serious side effects.

8.3 Risks of MRI

People are at risk for injury from the MRI magnet if they have pacemakers or other implanted electrical devices, brain stimulators, dental implants, aneurysm clips (metal clips on the wall of a large artery), metallic prostheses (including metal pins and rods, heart valves, and cochlear implants), permanent eyeliner or tattoos, implanted delivery pump, or shrapnel fragments. Welders and metal workers are also at risk for injury because of possible small metal fragments in the eye, of which they may be unaware. All subjects will be screened for these conditions prior to the study, and if they have any, they will not receive an MRI scan.

Gadolinium is a contrast agent approved for use with MRI by the FDA. No serious side effects have been associated with its use. The effect of gadolinium on the developing fetus remains partly unknown. Animal studies have shown a delay in development but no developmental abnormalities. Consequently, women of childbearing potential will be entered into this study only if an effective means of birth control is in use. A pregnancy test will be done prior to beginning the study and pregnancy tests will be done before MRIs are performed. The risks of an IV catheter include bleeding, infection, or inflammation of the skin and vein with pain and swelling. Symptoms from the contrast infusion are usually mild and may include coldness in the arm during the injection, a metallic taste, headache, and nausea. In an extremely small number of patients, more severe symptoms have been reported including shortness of breath, wheezing, hives, and lowering of blood pressure. Subjects should not receive gadolinium-based contrast agents if they have previously had an allergic reaction to them. Subjects will be asked about such allergic reactions before a contrast agent is administered. People with kidney disease are at risk for a serious reaction to gadolinium contrast called “nephrogenic systemic fibrosis” which has resulted in a very small number of deaths. If patients are older than 60 or have diabetes, kidney disease or liver disease, bloodwork to assess kidney function will be performed within 4 weeks before any MRI scan with gadolinium contrast. Patients may not receive gadolinium for a research MRI scan if kidney function is not normal. The long term effect of noise exposure from MRI is not known.

8.4 Risks of lumbar puncture

Adverse effects associated with lumbar punctures include brief pain or tingling paresthesias radiating down the lower extremity due to the needle brushing against a nerve. Should this occur, the needle can be repositioned. Mild lower back pain at the site of needle insertion following the procedure can occur; this can be managed with over the counter non-steroidal anti-inflammatory agents if needed. In approximately one third of patients, a post-dural puncture headache may develop and persist for a few days; in one in 50 to 200 lumbar punctures the post-dural puncture headache can last longer than 7 days. Generally this headache is not severe and resolves spontaneously within days - 2 weeks. Should the headache persist or be severe, a blood patch can be performed. An extremely rare complication of lumbar puncture includes temporary double vision related to abducens nerve palsy, and infection. Strict aseptic technique will be followed. Collecting additional 10-15 cc of CSF per procedure represents negligible risk (Evans, Armon et al. 2000). In humans the rate of CSF synthesis is approximately 21.5 cc/hour (Kimelberg 2004), or approximately 500cc/24hours, which represents

roughly 4 times the total volume of CSF in an adult patients. Therefore, the volume of 20-30cc of CSF that would be collected for both diagnostic and research purposes will be replenished in its entirety within approximately 1-1.5 hours after collection. Lumbar puncture may be done in the radiology department under fluoroscopic guidance for patient medical or scheduling needs. The radiation exposure during this procedure is 0.023 rem, which is well below the guideline of 5 rem per year allowed for adult research subjects by the NIH Radiation Safety Committee.

8.5 Risk of OCT

There are no known medical risks of optical coherence tomography.

8.6 Risk of electrophysiological studies

8.6.1 Risk of TMS

TMS is a safe procedure that has been used on thousands of people throughout the world, particularly the single-pulse TMS used in this study. Most people do not find the stimulation painful, but sometimes strong contractions of scalp muscles can cause discomfort or headache. Headaches usually go away promptly with nonprescription medication. The noise of the TMS magnet may damage hearing; therefore the subjects will be fitted with earplugs that must be worn during TMS. TMS can interfere with implanted medical devices and will not be done in people who have pacemakers, implanted pumps, or stimulators, such as cochlear implants or in people who have metal objects inside the eye or skull.

8.6.2 Risk of nerve conduction studies

The risks of the electrical stimulation using commercial isolated stimulators are low. Most subjects find electrical nerve shocks to be mildly uncomfortable; it is usually perceived as a brief stinging or tapping sensation. The intensities required for nerve conduction studies are usually well tolerated.

8.7 Risk Rehab Evaluation

The risk of physical injury in this series of noninvasive tests is minimal.

9. SUBJECT MONITORING

9.1 Parameters to be monitored

9.1.1 Expected Adverse Events:

Animal studies predict a low human toxicity profile for idebenone. This is supported by extensive experience including phase I trials in normal human volunteers and phase II and III trials in patients with Alzheimer's disease, FRDA, LHON, Duchene Muscular Dystrophy (DMD), cerebrovascular accident (stroke), multi-infarct dementia, and other neurodegenerative diseases (e.g. Huntington's disease), at doses comparable to those being used in this study. Based on the literature review of published data from these studies, the most frequently and consistently experienced adverse

reactions reported across these trials have been headache, diarrhea, nausea and dyspepsia. A complete list of previous adverse events, which may also be expected in this trial, may be found in the Investigator's Brochure and is summarized in section 7 of that document. In addition, medical events typical for clinical course of PP-MS (i.e. typical neurological signs/symptoms that patient experienced during pre-treatment baseline and their worsening as would be expected from the natural history of PP-MS) can be regarded as expected events in the course of the current trial.

9.1.2 Monitoring of adverse events:

The patient will be instructed to contact the investigator immediately should the patient manifest any sign or symptom perceived as serious during the period extending from performance of the first study procedure (e.g. drawing of a blood sample) up to and including 1 month after the last dose (telephone interview at month 37). After this period of time, the patient should report to the investigator only adverse events that are serious and perceived as possibly related to their participation in this study. Additionally, the patient will be instructed to contact the investigator immediately if he/she believes that he/she has fathered/conceived a child. Testing would be performed to verify that the subject or subject's partner was pregnant. If the pregnancy test were positive, the patient would be instructed to immediately stop taking the study drug. The patient or partner would be counseled and followed closely during the pregnancy by the NIH research team and would implement any recommendations made by the DSMB.

Patients will be physically examined by the investigator approximately every 6 months for the study duration. One week, one month (Mo 25) and 2 months (Mo 26) after initiation of dosing, patient's safety and change in neurological function will be assessed by telephone interview with an investigator (Figure 2).

Extensive laboratory monitoring (CBC with differential and Chemistry panel 20, which includes LFTs) will occur three times during the study duration: at month 25, 30, and 36 (Figure 2). Urinalysis and pregnancy test (for females with childbearing potential) will be performed every 6 months (before MRI).

All adverse events occurring within 1 month following the last administration of the study medication must be recorded on the Adverse Event Form irrespective of severity and seriousness, and whether or not they are considered related to the study medication. Additionally, all serious adverse events (SAE) brought to the attention of the investigator during the period starting from the day of performance of the first study procedure to the telephone interview on month 37, must be recorded and reported to the FDA in accordance with federal regulations and NIH procedures. Any SAE reported by the patient after month 37, will be subjected to expedited reporting only if judged to be related to the study treatment by the Investigator.

The collection of complete and accurate information is of paramount importance to allow a full evaluation of SAEs. Each SAE will be properly documented and followed up until the event is resolved, subsided, stabilized, disappeared or is otherwise explained or the study patient is lost to follow-up. Recurrent episodes, complications, or progression of the initial SAE will be reported as follow-up to the original episode, regardless of when the event occurs. Follow-up of reportable SAEs will be submitted to the FDA, IRB and Santhera Pharmaceuticals (Switzerland) Ltd. according to the

same timelines mandatory for initial reports, i.e. within 7 calendar days for fatal/life-threatening and 15 calendar days for all other SAE. An SAE that is considered completely unrelated to one previously reported, will be reported separately as a new event.

When a Serious Adverse Drug Reaction occurs during the clinical trial, the NINDS will provide Santhera Pharmaceuticals (Switzerland) Ltd. or designee with: a) primary safety information (i.e. short description including at least patient's study number, age and gender; reported SAE terms and causality assessment) at the time when the NINDS clinical director and the head of IRB are informed and no later than by Day 4; and b) copies of all Serious Adverse Drug Reaction reports concurrently with their submission to the FDA, including copies of any warning letters or other information affecting the safety and/or well-being of human subjects in research conducted under this MCRADA.

9.2 Toxicity tables/criteria to be used

Toxicity will be assessed according to the NCI Common Terminology Criteria for Adverse Events (CTCAE) version 3.0 (Publish date August 9, 2006). A copy of the Common Terminology Criteria for Adverse Events version 3.0 can be downloaded from http://ctep.cancer.gov/reporting/ctc_v30.html.

9.2.1 Definition of Adverse Event (AE)

An AE is “*any unfavorable and unintended diagnosis, symptom, sign (including an abnormal laboratory finding), syndrome or disease which either occurs during the study, having been absent at baseline, or, if present at baseline, appears to worsen.*” An AE is a term that is a unique representation of a specific event used for medical documentation and scientific analyses.

9.2.2 Severity of Adverse events

Grade refers to the severity of the AE. The CTCAE v3.0 displays Grades 1 through 5 with unique clinical descriptions of severity for each AE based on this general guideline:

- Grade 1 Mild AE
- Grade 2 Moderate AE
- Grade 3 Severe AE
- Grade 4 Life-threatening or disabling AE (SAE)
- Grade 5 Death related to AE (SAE)

Assessment	Definition
1 = Mild	Discomfort noted, but no disruption of normal daily activities; slightly bothersome; relieved with or without symptomatic treatment
2 = Moderate	Discomfort sufficient to reduce or affect normal daily activity to some degree; bothersome; interferes with activities, only partially relieved with symptomatic treatment.
3 = Severe	Discomfort sufficient to reduce or affect normal daily activity considerably; prevents regular activities; not relieved with symptomatic treatment.

9.2.3 Definition of Serious Adverse Event (SAE)

A serious adverse event is any untoward medical occurrence or effect at any dose, that:

- results in death,
- is life threatening,
- results in persistent or significant disability/incapacity,
- requires in-patient hospitalization[‡] or prolongation of existing hospitalization,
- results in cancer,
- is a congenital anomaly/birth defect in the offspring of a study subject,
- is deemed, by the investigator, an important or serious medical event that may jeopardize the patient or may require intervention to prevent one of the other outcomes listed above should be considered serious (i.e., intensive treatment in an emergency room or at home for allergic bronchospasm; blood dyscrasias or convulsions that do not result in hospitalization; or development of drug dependency or drug abuse.)

9.2.4 Assessment of causality

Every effort should be made by the investigator to explain each adverse event and assess its causal relationship, if any, to the study medication. The degree of certainty with which an adverse event can be attributed to the study medication (or alternative causes, e.g. natural history of the underlying diseases, concomitant therapy, etc.) will be determined by how well the event can be understood in terms of one or more of the following:

- Reaction of similar nature having previously been observed with this type of medication.
- The event having often been reported in literature for similar types of medication.
- Subject's underlying clinical state or other medical conditions
- Concomitant agents and/or therapies

The causal relationship, if any, to study medication will be defined by one of the following terms:

Assessment	Definition
Definitely	There is suspicion of a relationship between study medication and AE (without determining the extent of probability); there are no other more likely causes and study medication is suspected to have contributed to the AE
Probable	AE cannot be reasonably explained by other factors (i.e. clinical condition, environmental/toxic factors or other treatments)
Possible	AE can be reasonably explained by other factors (as mentioned above)
Unlikely	AE occurs within an unusual time frame of administration of study medication and can also be reasonably explained by other factors (as mentioned above)
Unrelated	There is no suspicion that there is a relationship between study medication and adverse event, there are other more likely causes and study medication is not suspected to have contributed to the AE

9.2.5 Treatment of adverse events:

Treatment of any AE is at the sole discretion of the investigator and according to current available best treatment. The applied measures will be recorded in the patient's chart.

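### The causality terms in section 9.2.4 overlap, and Definitely is looser than Probable on other causes, so the wording does not yield one term per event

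*Combined protocol and SAP*

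**What the plan says.** Section 9.2.4 gives five terms and requires one of them: "The causal relationship, if any, to study medication will be defined by one of the following terms". From top to bottom:

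- **Definitely** starts from suspicion: "There is suspicion of a relationship between study medication and AE (without determining the extent of probability". It adds that no cause is more likely and that the drug is suspected of contributing.
- **Probable** excludes any reasonable alternative, drawn from a closed list of clinical condition, environment or toxins, and other therapy. It is silent on suspicion and timing.
- **Possible** is the reverse of Probable: "AE can be reasonably explained by other factors (as mentioned above". Nothing on suspicion or timing is added.
- **Unlikely** brings timing in: "AE occurs within an unusual time frame of administration of study medication and can also be reasonably explained by other factors".
- **Unrelated** requires that nobody suspects a link, and further that "there are other more likely causes and study medication is not suspected to have contributed to the AE".

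No rule says what to do when two terms fit.

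Relatedness is used elsewhere. Under section 9.1.2, if the site learns of an SAE only once Month 37 has passed, it "will be subjected to expedited reporting only if judged to be related to the study treatment by the Investigator". Sections 9.1.2 and 18 require that, for a Serious Adverse Drug Reaction, the supplier receives initial information, including the causality assessment, no later than Day 4. Section 18 has the PI, with the CD, determine the relatedness of all SAEs to the research. None of these sections refers to the five terms or says which of them count as related.

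**The concern.** A causality scale should run from strongest to weakest and place each event once. This one does neither on its wording. The top label can go to an event that has a reasonable competing explanation, which the second label rules out. The middle label is met by any event with another reasonable explanation, whether or not the drug is suspected and whatever the timing. Two careful raters could therefore give the same event different labels and both follow the text.

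Safety and tolerability is the first primary goal in section 5.2. The causality assessment travels to the supplier, and section 7.6.1 moves the data to a natural history protocol for continued analysis, so the ratings may be read by people who were not present when they were made. The PI's patent interest (sections 16.1 and 22) has safeguards, but it is a further reason for clear definitions.

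**Working it through.** The plan gives no figure to reproduce. The check is logical.

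**Inputs, all from section 9.2.4.** Four yes/no facts per event: S, drug suspected; E, another reasonable explanation exists; M, another cause is more likely; T, unusual timing. I take M to imply E.

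**Definitions as written.** Definitely = S and not M. Probable = not E. Possible = E. Unlikely = E and T. Unrelated = not S and M.

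**Consequences that need no counting.**
- Since M implies E, not E implies not M. Every suspected event that meets Probable therefore meets Definitely, but not the reverse. The case S, E, not M is Definitely and cannot be Probable.
- Unlikely is Possible plus T, so every Unlikely event also meets Possible.
- Unrelated needs M, hence E, so every Unrelated event also meets Possible.

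**Counting.** Four facts with M implying E give 12 combinations. Leaving out the two with no suspicion and another explanation that is not more likely (hard to picture) gives 10.

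| S | E | M | T | Terms that fit |
|---|---|---|---|---|
| yes | no | no | no | Definitely, Probable |
| yes | no | no | yes | Definitely, Probable |
| yes | yes | no | no | Definitely, Possible |
| yes | yes | no | yes | Definitely, Possible, Unlikely |
| yes | yes | yes | no | Possible |
| yes | yes | yes | yes | Possible, Unlikely |
| no | no | no | no | Probable |
| no | no | no | yes | Probable |
| no | yes | yes | no | Possible, Unrelated |
| no | yes | yes | yes | Possible, Unlikely, Unrelated |

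One term: 3. Two: 5. Three: 2. Total 3 + 5 + 2 = 10.

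**Effect on a related/not related split.** The plan sets no cut-off, so each is an assumption. A case is open if its terms fall on both sides.

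| Lowest term counted as related | Open, of 10 | Open, of 12 |
|---|---|---|
| Definitely | 4 | 4 |
| Probable | 2 | 2 |
| Possible | 4 | 5 |
| Unlikely | 2 | 2 |

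Without the assumption that M implies E there are 16 combinations, and the open counts are 4, 4, 7 and 4. No cut-off gives zero. The totals depend on which cases are admitted, so they show only that the ambiguity exists.

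**Study procedures.** Probable introduces its list of other factors with i.e. and names clinical condition, environmental or toxic factors, and other treatments. Lumbar puncture, apheresis and contrast are not named. The opening text of 9.2.4 uses an open list of alternative causes. The two should agree.

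**The case against.** The best defence is that 9.2.4 describes a degree of certainty, informed by prior reactions, the literature, the patient's state and concomitant agents, and that raters would use the labels in their usual order. Unlikely reads naturally as Possible with a timing condition added, so the more specific term would win. That reading helps. If Unlikely and Unrelated displace Possible, the open cases at a Possible cut-off fall from 4 to 1: the suspected, equally explained event with unusual timing, which still fits both Definitely and Unlikely. But the rule is unwritten, and it does not repair Definitely.

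Some stronger readings are tempting and are not supported:

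- *That expedited reporting or supplier notice is decided by the five terms.* Sections 9.1.2 and 18 leave relatedness to judgement and never tie it, or Serious Adverse Drug Reaction, to the scale. The missing link is part of the point; a proven reporting failure is not.
- *That SAEs reported after Month 37 must have unusual timing.* The rule turns on the date of the report, not of onset, so an on-treatment event reported late also falls there. Patients are also asked to report at that stage only serious events that they see as possibly related.
- *That puncture headaches would distort the count of related AEs.* Section 11.2 plans only descriptive safety analysis, with no table by relatedness, and an ordinary headache of a few days is not serious.
- *That rating an unexplained, unsuspected event as Probable is itself an error.* It is a conservative default, and worth keeping in an open-label study.

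Safeguards that do not depend on the rating also stand. Section 9.1.2 says "All adverse events occurring within 1 month following the last administration of the study medication must be recorded on the Adverse Event Form". SAEs up to the Month 37 call are recorded and reported under their own sentence there. The DSMB receives all SAEs within 7 days (section 16.2.3). The IRB and CD receive them within 7 days, with two named exceptions (section 18).

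**Conclusion.** The definitions are wrong as written. This is more than missing detail: a stated rule requires one term, and 7 of the 10 logical cases fit two or three. The fault of order is confined to Definitely against Probable, on alternative causes. The overlap centres on Possible. Both follow from the text, given that a more likely cause counts as a reasonable explanation.

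The consequence is modest. The gap between the scale and the word related leaves the causality assessment sent to the supplier, and the late-SAE judgement, without a fixed meaning. No efficacy analysis and no planned safety table is affected. Section 7.6.1 stops the study for futility and closes enrolment, so few or no SAEs may be involved. A cheap correction is worth considering.

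**What to change.** Replace the table in 9.2.4 with:

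- **Definitely:** meets Probable, plus confirming evidence such as recurrence on re-dosing.
- **Probable:** plausible timing and no other reasonable explanation.
- **Possible:** drug contribution suspected, plausible timing, another reasonable explanation exists.
- **Unlikely:** unusual timing and another reasonable explanation.
- **Unrelated:** no suspicion, and a more likely other cause identified.

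Add two rules. If more than one term fits, the most specific applies; say explicitly that Definitely goes before Probable and Unrelated before Unlikely. An event with no identified cause is rated at least Possible, and any event that fits no term is rated Possible. Lack of suspicion alone then never makes an unexplained event Unrelated.

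Applied to the table above, in row order, this gives Probable, Possible, Possible, Unlikely, Possible, Unlikely, Probable, Possible, Unrelated, Unrelated: one term each, with Probable becoming Definitely where confirming evidence exists. The two omitted combinations become Possible (plausible timing) and Unlikely (unusual timing).

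Name study procedures (lumbar puncture, apheresis, contrast) among the other factors. State in sections 9.1.2 and 18 that Possible or higher counts as related, including for Serious Adverse Drug Reaction.

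Cost: one amended table and two cross-references. Some unexplained events will count as related without suspicion, which is the intended caution. Any re-rating would come after the parent result is known, so the independent medical monitor should do it, with the original ratings kept alongside.
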